### 13.0 Provisions to Monitor the Data to Ensure the Safety of Subjects

[name] or his designee, should he be unavailable, will be responsible for reporting all unanticipated problems or AEs to the IRB. The PI or some study team member will be present for each patient and record AE's real time. Soterix will be responsible for reporting any unanticipated device-related AE's to FDA. All screening data will be kept in a file on Redcap. Screening data collected from participants who do not qualify for the study will be securely destroyed.

[name], who is a board certified neurologist and psychiatrist, and [name] will oversee the device testing and technical use of the Soterix system.

An independent Safety Monitoring Committee (SMC) will be formed to advise the study investigators. The SMC will review and evaluate accumulated study data to ensure safety. They also will make recommendations concerning continuation, modification, or termination of any of the taVNS studies. It will be composed of several prominent COVID experts and [name], MUSC associate professor and assistant provost who has extensive VNS, TMS, and tDCS experience.

The SMC will be notified immediately of any and all SAE's. We will report to the IRB the number of treatments held for HR or redness, discomfort.

Drs. [name] or [name] will obtain informed consent, during which participants or their guardians are fully advised on the research procedures to be used, the amount of time required of them, the possible risks and benefits of the procedures, their right to refuse their infant's participation in the study without prejudice, their right to terminate participation at any moment without prejudice, and the name and telephone number of the principal investigator. The legal guardians of all subjects will be required to have legal ability to consent.

Regarding confidentiality, subjects are informed that the information they provide, as well as participation in the study, will be kept strictly confidential, with access limited to the research staff. The identity of subjects in databases will be protected with alphanumeric codes. All data will be kept in locked file cabinets or on secure servers designed for use and access by Brain Stimulation Lab members only.

### 14.0 Withdrawal of Subjects

- *Describe anticipated circumstances under which subjects will be withdrawn from the research without their consent, including stopping participation for safety reasons.*

taVNS has been a very safe procedure and we do not anticipate subject withdrawal due to taVNS side effects. We will be monitoring each session and if a patient is extremely hemodynamically sensitive to the device we might consider terminating. Severely worsening of symptoms would be another reason (for example, worsening of headaches). VNS is antidepressant, antinociceptive, anti-inflammatory and anxiolytic so we do not anticipate worsening in these areas.

- *Describe any procedures for orderly termination of subjects by investigator.*

Any termination would involve online video conversations with subjects and follow the patterns used for in person documentation of the reasons and ensuring that patients have understanding and medical follow-up.

- *Describe procedures that will be followed when subjects voluntarily withdraw from the research, including partial withdrawal from procedures with continued data collection.*

As with all research, a subject can withdraw from research at any time. We will honor this and make sure the patient is safe and has good options and care and will ship the device back to MUSC.

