**6.0 Number of Subjects**

We will recruit 30 COVID positive adults in order to have 24 completers.

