## **12.0 Data Management**

All data will be stored in the Redcap database. The blind will be kept by the MUSC RA, but they will be blinded as well. Soterix will set the active or sham control from the company after being instructed by the MUSC RA about the randomization code number for that patient, but MUSC will have the unblind in terms of emergency.

Information about the participant (including their identifiable private information and/or any identifiable biospecimens) may have all of their identifiers removed and used for future research studies or distributed to other researchers for future research without additional informed consent from them or their legally authorized representative.

In rare cases, the device manufacturer, Soterix, may need access to minimal PHI (such as name, phone number and address) in the event there is a device malfunction. Well-trained MUSC staff will make every attempt to resolve any issues before putting Soterix in direct contact with the participant.

At a high-level analysis, we will compare the group changes in neuropsychiatric questionnaires in active versus sham taVNS using repeated measures ANOVA from baseline to immediately after last treatment and then as well over the 3-month follow-up.

Power analysis on primary outcome: As there is no real data yet on taVNS effects on NeuroCOVID patients, it is difficult to perform a formal power analysis. The repeated measures design in 15 active and 15 sham patients will allow us to detect differences with a large or moderate effect size to be used for calculating power and sample size for subsequent trials.

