### Potential decrease in heart rate:

Ear stimulation may slow heart rate. In rare cases (less than 1%) decreased blood pressure or fainting may occur. We expect no significant changes in heart rate or blood pressure, or fainting may occur. For the initial sessions all subjects will be stimulating while they are seated, never standing. We expect no significant changes in heart rate or blood pressure, but if this occurs, the study team will evaluate the situation and either decide that the patient should be dropped from the study, or do all sessions laying on a couch, or with lower doses.

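### Patients may be withdrawn for worsening or a reaction, with no provision for further ratings and no missing-data rule, so the active-sham comparison could be biased in either direction

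*Combined protocol and SAP*

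**What the plan says.** Section 14.0 (Withdrawal of Subjects) answers a template question about withdrawing subjects without their consent. It gives two reasons. For haemodynamics, "if a patient is extremely hemodynamically sensitive to the device we might consider terminating". For symptoms, "Severely worsening of symptoms would be another reason (for example, worsening of headaches". The same answer expects few such cases: "we do not anticipate subject withdrawal due to taVNS side effects".

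Section 15.0 (Potential decrease in heart rate) says that, if heart rate or blood pressure changes, the team will "either decide that the patient should be dropped from the study, or do all sessions laying on a couch, or with lower doses". It also says: "In rare cases (less than 1%) decreased blood pressure or fainting may occur".

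On what happens after withdrawal, section 14.0 covers documenting the reasons, medical follow-up, the patient's safety and care, and return of the device. The template's prompt on voluntary withdrawal asks about partial withdrawal with continued data collection. The reply does not take that up, and nothing is said about ratings after an investigator-initiated withdrawal.

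Section 6.0 gives the only figures on loss: "We will recruit 30 COVID positive adults in order to have 24 completers". Section 12.0 compares the arms "using repeated measures ANOVA from baseline to immediately after last treatment" and over the 3-month follow-up. It names no analysis population, missing-data rule or sensitivity analysis.

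**The concern.** One permitted reason for withdrawal is a bad value of something the trial measures. Headache is listed among the target symptoms in section 1.0 (Aim 1) and in the inclusion criteria of section 5.0, and change in neuropsychiatric symptoms stands under the primary outcome in section 4.0.

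The reasons may also be related to arm. Section 15.0 lists headache as a possible effect of stimulation. By section 3.0, active delivers 60/(60+30) × 60 min = 40 minutes of current per session, while sham delivers 20 + 20 = 40 seconds. Reactions are therefore more plausible under active in the blinded phase. Symptoms left without active treatment may worsen under sham, and after week 2 both arms receive active stimulation, so losses could fall on either side.

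If withdrawn patients are not rated and the ANOVA is run on complete cases, those analysed are selected on outcome. A patient withdrawn in week 3 or 4 would also lose the ratings already given in the randomised phase. Section 12.0 intends the effect size to be used in sizing later trials, so a distortion would carry forward.

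**Working it through.** **Inputs from the documents.** 30 recruited and 24 completers (6.0); 15 per arm (12.0); no withdrawals for side effects anticipated (14.0); low blood pressure or fainting in under 1% (15.0).

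**Not in the documents, so assumed.** The number of outcome-related withdrawals, their arm, how closely the trigger tracks the final rating, and the error rate (two-sided 5%).

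**Step 1: the plan's own figure.** Implied loss = (30 − 24)/30 = 6/30 = 20%, and 24/(1 − 0.20) = 30. This agrees, but it is circular, because the 20% is derived from the same two numbers. The six are not divided by cause or arm. Section 12.0's statement on detectable effects cannot be reproduced: it gives no error rate, power, SD or correlation.

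**Step 2: losing exactly the worst outcomes.** Simulation of 15 v 15 standard normal outcomes (higher = worse), no true effect, 100,000 runs. The k worst are removed and the rest compared by t-test, as a stand-in for a complete-case repeated measures ANOVA. Shift = mean(sham kept) − mean(active kept); positive favours active.

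| Removed, active / sham | Shift (SD) | Two-sided false positives |
|---|---|---|
| 0 / 0 | 0.00 | 4.9% |
| 1 / 0 | 0.13 | 7.1% |
| 2 / 0 | 0.23 | 10.9% |
| 3 / 0 | 0.33 | 15.8% |
| 2 / 1 | 0.11 | 8.6% |
| 1 / 1 | 0.00 | 6.8% |
| 2 / 2 | 0.00 | 8.3% |
| 3 / 3 | 0.00 | 9.5% |
| 0 / 1 | −0.12 | 7.0% |
| 0 / 2 | −0.23 | 10.7% |
| 0 / 3 | −0.33 | 15.7% |

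Equal loss leaves the mean contrast unbiased. The error rate still rises, because trimming shrinks the spread from which the standard error is computed.

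**Step 3: a weaker link.** If withdrawal is triggered by something that correlates r with the final rating, the shift is about r times the value above (for example 0.6 × 0.33 = 0.20; 0.3 × 0.13 = 0.04). Simulated, for 1, 2 and 3 removed from one arm only:
- r = 0.3: 0.04, 0.07, 0.10 SD
- r = 0.6: 0.08, 0.14, 0.20 SD

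**Step 4: how often a reaction might occur.** Reading the stated rate as 1% per patient, P(at least one in 15) = 1 − 0.99^15 = 14%, and P(at least two) is about 1%. Haemodynamic events alone would rarely cost an arm more than one patient. Losses of two or three would need symptom worsening as well.

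**Step 5: scale.** With 12 v 15 analysed, the standard error of the contrast is √(1/12 + 1/15) = 0.39 SD. The largest shift, 0.33 SD, is a little under one standard error; 0.20 SD is about half of one.

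**Step 6: after the change.** If everyone withdrawn is still rated and analysed as assigned, the 0 / 0 row applies: shift 0.00 SD, error 4.9%.

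**The case against.** Several stronger readings are tempting, and the documents do not support them.

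- *Ratings stop on withdrawal.* A reader might infer this, but no section says so. The text is silent, and the prompt on continued data collection concerns voluntary withdrawal.
- *Patients who react are removed.* Withdrawal is discretionary. Of the three options in section 15.0, two keep the patient in, and the symptom criterion is confined to severe worsening.
- *Stopping stimulation always means leaving the study.* Section 13.0 counts treatments held, and section 15.0 speaks of stopping stimulation for burns without mentioning exit. The two are distinguished in places, though not where withdrawal is described.
- *The plan specifies a completer analysis.* It does not. Section 12.0 refers to 15 per arm, which is all 30. Omitting incomplete cases is how the named method usually works, not something the plan states.
- *Tolerability will be overstated.* Dropout, syncope and other adverse events are reported outcomes (section 4.0), so these patients still count.
- *The comparison is biased towards active.* That needs unequal, outcome-related loss combined with a complete-case analysis. Six losses split evenly give about 0, and heavier loss from sham would work against active.

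These objections stand. It is also fair that section 4.0 calls the trial a pilot with largely descriptive outcomes. That lowers the stakes but does not remove them: efficacy is named in Aim 1 and the effect size is meant for planning later trials. Reporting dropout discloses the loss but does not repair the comparison.

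**Conclusion.** The concern holds in conditional form. Followed as written, the plan permits loss of patients because of their outcome, makes no provision to keep rating them, and names an analysis that in its standard form leaves them out. Whether this biases the comparison, and in which direction, depends on losses that the documents do not quantify.

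The range rests on assumed one-arm losses of 1 to 3 of 15: about 0.04 to 0.20 SD for a trigger-outcome correlation of 0.3 to 0.6, with 0.33 SD as the extreme. It falls to about 0 when loss is equal. The extreme should not be read as an expected value, since the implied 20% loss covers all causes. This is a cheap improvement, not a fatal flaw.

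**What to change.** - **Sections 14.0 and 15.0:** separate stopping stimulation from leaving the study. State that anyone who stops stimulation, for whatever reason, is asked to continue the scheduled online ratings unless they decline. Leave the clinical reasons for stopping stimulation unchanged.
- **Section 12.0:** analyse all randomised patients in their assigned arm using every available rating, for example with a likelihood-based mixed model in place of a complete-case repeated measures ANOVA. For patients who decline further ratings the model still assumes that the missing values are predictable from the observed ones. A short sensitivity analysis giving unfavourable values to those withdrawn for worsening would show how much that assumption matters.
- **Reporting:** give withdrawals by arm and reason.

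The cost is protocol and consent wording, some reminders, and a slight burden on patients. Ratings are already online, and by section 18.0 devices go back at week 4 while ratings run to week 12, so rating patients who are off stimulation is already part of the trial's routine.

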## 15.0 Risks to Subjects

### Ear Stimulation:

Ear stimulation is safe, however there are some risks associated with stimulating the ear: There may be local discomfort. This will likely be temporary. In extreme cases burns might occur. We will video monitor any potential burns and will stop stimulation and advise subjects to apply vitamin E cream. Tissue surrounding the ear may be sensitive, sore or feel slight numbness. Hopefully this will be temporary and will go away after stimulation is turned off.

### Potential Headache, Dizziness, and Facial Pain:

Ear stimulation might cause headaches or face pain, which should resolve shortly after treatment.

### Safety in case of pregnancy

This protocol will exclude pregnant women. The risks of using taVNS with pregnant women are currently unknown. If in the screening and consent a patient is a woman of childbearing age, we will send them by mail a urine pregnancy test. They will need to complete this and show the negative result to the RA on doxy.me.

### Potential decrease in heart rate:

Ear stimulation may slow heart rate. In rare cases (less than 1%) decreased blood pressure or fainting may occur. We expect no significant changes in heart rate or blood pressure, or fainting may occur. For the initial sessions all subjects will be stimulating while they are seated, never standing. We expect no significant changes in heart rate or blood pressure, but if this occurs, the study team will evaluate the situation and either decide that the patient should be dropped from the study, or do all sessions laying on a couch, or with lower doses.

### Unknown Risks:

There is always the possibility of other risks for a relatively new technology. The Study team will let the participant know if they learn anything that might make the participant change their mind about participating in the study.

### Loss of Confidentiality:

There is a risk of a loss of confidentiality of personal information. Subjects are informed that the information they provide, as well as participation in the study, will be kept strictly confidential, with access limited to the research staff. The identity of subjects in databases will be protected with alphanumeric codes. All data will be kept in locked file cabinets or on secure servers designed for use and access by Brain Stimulation Lab members only.

### Potential Randomization Risk:

The treatment a subject receives may prove to be less effective or to have more side effects than the other study treatment(s) or other available treatments.

### Questionnaire Risk:

There are no anticipated risks to the participant. However, the participant may feel that some of the questions we ask are stressful or upsetting. If they do not wish to answer a question, they may skip it and go to the next question, or they may stop immediately. Also, being assessed for study entry, including the possibility that they may not meet criteria for entering the study may be distressing. If they become upset or distressed as a result of their participation in the research project, the research team will be able to arrange for a one on one meeting with our team psychiatrist.

Our commitment to patients is to take all reasonable steps to help them find treatments for worsening psychiatric symptoms. If the subject's psychiatric conditions worsen (specifically suicidality or suicide ideation), we will provide the National Suicide Prevention Hotline call or text number ([name]) to the subject or advise the subject to go to the nearest Emergency Department or call 911.

### **16.0 Potential Benefits to Subjects or Others**

A strength of this proposal is that it will allow us to pivot in the directions of greatest need in one year with a multitude of potential therapeutic targets and benefits, once initial feasibility and efficacy of the taVNS home therapy protocol has been established. The research team is experienced and are leaders in neuromodulation research and are thus uniquely capable of successfully shepherding this pilot work into a funded clinical trial. Invasive cervical VNS is FDA approved for epilepsy and depression. Noninvasive cervical VNS is FDA approved for cluster headaches. We have seen anxiolytic and antidepressant effects of taVNS. There is legitimate prospect of benefit for NeuroCovid symptoms although this is still experimental. All subjects will get the active open treatment for weeks 2-4.

### **17.0 Sharing of Results with Subjects**

There is no plan to inform subjects of the results of the study, but they can always contact the research staff and ask. If there are significant new findings during the course of the study, they will be notified.

### **18.0 Devices**

Soterix, the device company, will ship the device to the RA's at MUSC. The MUSC RA will then ship the device to the subject (along with a urine pregnancy test if that is indicated.) The subject is in charge of storing the device while it is at their house. The subject will be informed on how to manage and care for the device prior to receiving the device through a video. The study team will then hold training sessions with the subject. At the end of the 4 weeks the subject will need to ship the device back to MUSC with pre-paid packaging and a label. If the device is damaged at home, we will ship another device and have them ship the damaged unit back. Because the device can be remotely controlled, we will inform patients that the device becomes a 'brick' after the 4th week and has no resale value and cannot be used further.

Importantly, the device is programmed remotely, and subjects cannot administer more than the indicated dose. That is, they cannot stimulate for more than the two one-hour sessions each day. If a subject falls asleep with the device on it will turn itself off automatically.

We are asking for a Non-significant risk determination of this device. IRB 1 has consistently given NSR status for all prior taVNS studies at MUSC, including studies in stroke patients ([name]), brain damaged newborns learning to feed ([name]), Parkinson's Disease ([name], [name]) and healthy volunteers ([name]).

